Identifying factors that can potentially interrupt this cycle has significant implications for public health. Growing evidence indicates that DHA supplementation improves maternal stress reactivity during pregnancy and protects neurodevelopment of the offspring, especially in the context of high levels of stress exposure. We propose a program of research that aims to translate such findings to address the significant health disparities for African American women and children. In the following section we present preliminary evidence for the efficacy of prenatal fatty acid supplementation on maternal perceived stress and stress reactivity in this high-risk population.

Preliminary support for hypotheses

We recently completed the first randomized controlled trial of DHA supplementation among pregnant African American women living in stressful, low-income, urban environments (for a full report see Keenan et al., in press, *Obstetrics & Gynecology*). Sixty-four pregnant women were recruited from the Obstetrics Clinics at the University of Pittsburgh. Inclusion criteria were: African American race, age between 20 and 30 years, 16-21 weeks of gestation, Medicaid insurance or Medicaid eligible, and low levels of DHA consumption as defined as less than two fish servings per week. Exclusion criteria were medical complications (e.g., gestational diabetes, pre-eclampsia), regular use of steroid medications, use of blood thinners or anti-coagulants, use of psychotropic medications, current BMI >40, and allergy to iodine and/or soy. Participants were reimbursed on an accelerated schedule with \$40 for their first visit and an increase in payments of \$10 for each subsequent visit. The Institutional Review Boards of the Universities of Chicago and Pittsburgh approved all study procedures. Once enrolled, women were randomly assigned to receive the omega-3 nutritional supplement (n = 43) or a corn and soybean oil placebo (n = 21) beginning at enrollment and up through the end of pregnancy. Women received supplement via two gel capsules providing: 450 mg of DHA; 40 mg of docospentaenoic acid (DPA) and eicosatetranoic acid

[figure not shown]
(ETA); 90 mg of eicosapentaenoic acid (EPA); and 15 IU of Vitamin E. Randomization was conducted by the pharmacy at the University of Pittsburgh, thus ensuring that participants and investigators were blinded to the group to which the participants were assigned.

[figure not shown]

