Cortisol response to a social evaluative stressor was measured at baseline, 24 and 30 weeks of gestation. Saliva was collected at three time points at the baseline, 24 and 30 week assessments: 20 minutes following arrival to the lab, and 20 and 45 minutes post-TSST. Participants completed questionnaires assessing perceived stress, stressful life events, and symptoms of depression at baseline, 24, and 30 weeks of gestation. Research assistants contacted participants by phone 3 times per week to ask the time of day that supplement was taken, and collected data on perception of taste, and possible gastrointestinal side effects.

[figure not shown]
Of the 64 participants who completed the baseline assessment, 4 (6.3%) withdrew from the study. Two participants randomized to placebo withdrew: one miscarried and the other withdrew due to mood changes, and two participants randomized to active supplement withdrew: one reported headaches and the other upset stomach. Forty-seven participants (73.4%) attended all three sessions. Thus, acceptability and feasibility were high, and retention was very good.

The first goal was to examine group differences in level of depression, negative life events, and perceived stress by conducting analyses of variance for each measure, controlling for the other two measures. At baseline and 24 weeks of gestation, there were no group differences in any of the three measures. By 30 weeks, perceived stress was significantly lower among the participants receiving supplementation compared to those receiving placebo, controlling for negative life events and depression scores at 30 weeks (F [1,47] = 5.06, p = .029, Figure 2).

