In addition to associations between DHA supplementation and prenatal stress, we observed significantly higher birth weights among neonates born to women receiving DHA compared to placebo controlling for gestational age (3,174 grams versus 2,889 grams, p = .018) and greater likelihood of having a 1-minute Apgar score of 9 (odds ratio = 5.99 [95% Cl = 1.25 - 28.75], p = .025, controlling for birth weight and gestational age). Finally, 13% of neonates of mother receiving DHA supplementation were born prior to 37 weeks, compared to 22% of mothers received placebo; a difference that did not reach the level of statistical significance in the pilot study, but is clinically meaningful.

In summary, the data from our preliminary study are compelling in terms of the potential impact on health disparities in maternal and infant health, a significant public health problem that is poorly understood. We now seek to expand on these preliminary findings by conducting a more rigorous assessment of prenatal DHA supplementation on maternal and infant health by increasing the number of participants to 162, beginning supplementation earlier in pregnancy, adding additional measures of maternal health and stress response during pregnancy, increasing the frequency of assessment, assessing DHA levels in red blood cells at each visit, and including multiple postnatal assessments of infant neurodevelopment. The proposed study offers an opportunity for replication and to test the impact of supplementation on infant functioning and, if effects are observed, whether they are mediated by changes in prenatal stress.

APPROACH

Participants

One hundred-sixty-eight pregnant, African American, women will be recruited from the University of Chicago obstetric clinic. Inclusion criteria will include: age between 18 and 34 years, household receipt of public assistance (e.g., Medicaid insurance) due to low-income, and low levels of DHA consumption as defined as less than two fish servings per week. Exclusion criteria are reports of known medical complications, regular use of steroid medications, alcohol, cigarettes, or illegal substances (by maternal report), use of blood thinners or anti-coagulants, use of psychotropic medications, BMI >40, and allergy to iodine and/or soy. Participants may be excluded if medical complications arise after enrollment. Neonates with significant medical complications will be maintained in the study.

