Nordic Naturals adheres to high standards on safety and purity by setting low levels of allowances for peroxides, heavy metals, dioxins, furans, and PCBs. A certificate of analysis is provided for every batch of ProDHA based on both an internal analysis and an analysis conducted by an independent laboratory.

The investigational pharmacy at the University of Chicago will use computer generated random assignment of ID numbers to active supplement or placebo in blocks of 18: 12 ID numbers will be randomized to active supplement and six to placebo. In order to maintain the double-blind, the pharmacist will divide each randomization block of 18 ID numbers into groups of three: six ID numbers were assigned to group A (placebo) and the remaining 12 will be assigned to either group B or C, both of which will receive identical doses of active supplement. This approach will allow the pharmacist to randomize on a 2:1 ratio without having the unbalanced design break the blind. Once the study is complete and the blind broken, the two groups receiving identical doses of active supplement will be combined for analyses.

Each participant will receive a 6-week supply. She will bring any unused DHA back to her next visit; pills will be double counted at that time as an additional method for monitoring compliance. At each visit she will receive the next supply. Research assistants will contact participants by phone 3 times per week to ask the time of day that supplement was taken, and data on perception of taste, and possible gastrointestinal side effects. At each laboratory visit research assistants will interview participants about diet over the past 24 hours and past two weeks to determine intake of sea fish or other DHA rich foods (e.g., flax seed).

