In addition to changes in cortisol, heart rate and blood pressure (BP) will be assessed in response to the TSST as indirect measures of sympathetic-adrenal activation. Heart rate and BP will be measured throughout the period of acclimation, during the TSST, and during recovery (see Figure 5). Heart rate variability (HRV) will be measured from a continuous time series of inter-beat intervals. Prior to calculating estimates of HRV, the digitalized ECG signals will be examined and artifactual detections of R-wave occurrences will be corrected. The square root of the mean of successive differences (RMSSD) in inter-beat intervals will be used as a time-domain estimate of HRV. Inter-rater reliability for the editing of artifacts will be assessed using 40 x 5 min epochs (10 per participant for 4 randomly selected participants).

Infant outcomes. We include measures of infant outcomes that have been shown to be associated with DHA (e.g., cognition) and maternal stress during pregnancy (e.g., temperament, behavioral and emotional regulation and stress reactivity). In addition, we selected measures that would be comparable to existing studies of infant stress reactivity. We will collect birth outcomes from the medical record including type of delivery, gestational age, weight, length, head circumferene, apgar scores, cord problems, and meconium aspiration, extended hospital stay or NICU admission, etc. The Neonatal Behavioral Assessment Scale (NBAS; Brazelton & Nugent 1995) will be administered within the first month to assess the neurodevelopment by sampling a broad range of behaviors including reflexes, state changes, attention, arousal, and regulatory capacities such as intensity and duration of distress, latency to distress and self-soothing. The principal investigator was trained and certified by the Brazelton Institute. In our own work we have demonstrated that the NBAS elicits a cortisol response in neonates (Keenan Gunthorpe, & Grace, 2002; Keenan, Grace & Gunthorpe, 2003), and have observed associations between behavioral and cortisol response to the NBAS and prental stress (Keenan, Gunthorpe & Grace, 2007).

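### The only side-effect question covers gastrointestinal symptoms; headache and pregnancy loss have no named route of capture, and no comparison of side effects, losses or withdrawal reasons by arm is planned

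*Combined protocol and SAP*

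**What the plan says.** All references are to the combined protocol and SAP.

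- **Side-effect enquiry (Methods, Nutritional Supplement).** Research assistants telephone three times a week "to ask the time of day that supplement was taken, and data on perception of taste, and possible gastrointestinal side effects". The pilot's calls, described under Preliminary support for hypotheses, had the same content.
- **Pilot experience (same section).** "Of the 64 participants who completed the baseline assessment, 4 (6.3%) withdrew from the study". On placebo, one woman stopped after a miscarriage and one for mood changes. For the active arm the text reads: "two participants randomized to active supplement withdrew: one reported headaches and the other upset stomach".
- **Mood (Maternal Psychosocial Stress; Table 1; Hypotheses 1 and 2).** Depression is scored with the EDS/EPDS and anxiety with the STAI. Prenatal change in both is analysed by repeated measures ANOVA, in a paragraph that sets supplement group as the between-subjects factor. Postpartum depression and anxiety are compared between arms by ANOVA.
- **Medical record (Infant outcomes).** Birth outcomes are abstracted, including type of delivery and then "gestational age, weight, length, head circumferene, apgar scores, cord problems, and meconium aspiration, extended hospital stay or NICU admission, etc". Miscarriage, stillbirth and neonatal death are not named, although the list is open-ended.
- **Complications after enrolment (Participants).** They are mentioned only as a possible ground for excluding a woman. No recording or count by arm is described.
- **Analysis (Hypotheses and Analyses, through Missing data).** No comparison of side effects, adverse events, pregnancy losses or withdrawal reasons between arms appears.

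**The concern.** The call content was carried over from the pilot unchanged, although one of the two pilot withdrawals on active supplement was for a symptom the call does not ask about. A symptom that nobody asks about, and that does not make a woman stop, is recorded only if she volunteers it and someone writes it down. Such reporting is incomplete and cannot be reliably rebuilt after the trial.

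The second half of the gap is analytic. The gastrointestinal answers are collected three times a week, yet no table or test uses them. Nor does the plan say how a pregnancy that ends in loss is counted when gestation and birth weight are compared under Hypothesis 2. This trial differs from the pilot in "beginning supplementation earlier in pregnancy", so more early losses could fall within follow-up; the documents give no rate for this.

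At stake is whether the trial can report harms for the 112 women planned for active supplement through the end of pregnancy. Capture matters in both directions: losses on placebo that go uncounted could hide a benefit.

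**Working it through.** **1. Reproduce the pilot figure.** The pilot allocated 43 + 21 = 64 women. Withdrawals: 4/64 = 6.25%, which rounds to the stated 6.3%.

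**2. Compare withdrawals by arm.** Active 2/43 = 4.7%; placebo 2/21 = 9.5%; Fisher exact p = 0.59. The pilot shows no excess on active.

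**3. Match each pilot reason to what the new trial asks and compares.**

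| Pilot reason | Arm | Elicited in the new trial? | Planned comparison by arm? |
|---|---|---|---|
| Upset stomach | Active | Yes, phone call | No |
| Headaches | Active | No stated question | No |
| Mood changes | Placebo | Yes, EDS/EPDS and STAI | Yes |
| Miscarriage | Placebo | Not named; open-ended record list | No |

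The call itself matches 1 of 4 reasons. Across all described procedures, 2 of 4 are elicited and 2 of 4 have no stated question or named item. Only 1 of 4 has a planned comparison by arm; 3 of 4 have none.

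**4. Scale to this trial.** Inputs: 112 active + 56 placebo = 168 (Participants); two pilot withdrawals among 64 for headache or miscarriage.

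- Pooled: 168 × 2/64 = 5.25, about 5 withdrawals.
- By arm, as a check: headache 112 × 1/43 = 2.6; miscarriage 56 × 1/21 = 2.7; total 5.3. The two agree because both trials allocate about 2:1.
- Range: the exact (Clopper-Pearson) 95% interval for 2/64 is 0.4% to 10.8%. Multiplied by 168, this gives about 0.6 to 18.

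**5. Headache on active alone.** 1/43 = 2.3% (exact 95% interval 0.1% to 12.3%). If 1/43 held, the chance of at least one such withdrawal among 112 women is 1 − (42/43)^112 = 93%.

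Steps 4 and 5 count withdrawals only. The documents give no rate for headaches or other symptoms that do not lead to withdrawal, so that larger group cannot be sized.

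**The case against.** The strongest reply is that the pilot, using the same calls, recorded all four withdrawal reasons and reported them by arm. Reasons for stopping surfaced without a dedicated question, and would probably do so again. Staff speak to each woman three times a week, so a miscarriage would hardly go unnoticed, and the open-ended record list gives pregnancy loss a possible route. This stands, and it limits the point. The five or so withdrawals in the working are not five events that would be lost. What the reply does not cover is symptoms short of withdrawal, and the absence of any plan to tabulate what is learned.

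Four stronger readings are tempting and should be resisted.

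- **That most of the events seen in the pilot would go unasked, because three of four were not gastrointestinal.** Mood is measured with two scales and analysed by group, so the count is two of four. A mood change arising between visits in a woman who then stops could still be missed by both the carried-forward and the complete-case analysis, but this does not make mood unmeasured.
- **That the supplement caused these events.** The miscarriage and the mood change were both on placebo. Headache was the only non-gastrointestinal reason on active, in one woman.
- **That losses will be dropped from the analysis as withdrawals.** The pilot counted its miscarriage as a withdrawal, but the new plan states no such rule, and its missing-data section invokes intention to treat for non-compliers. The plan is silent on losses.
- **That the trial has no adverse-event procedures at all.** The supplied text describes none, but a separate safety document may exist, and consent pages were removed from what was supplied.

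**Conclusion.** The concern holds as a limited gap in capture and reporting. In the supplied text the only side-effect question is gastrointestinal. Headache has no stated question, pregnancy loss is not a named record item, and no side effect, loss or withdrawal reason is to be compared by arm. Three of the four kinds of event that ended participation in the pilot therefore have no planned comparison, and two of the four have no stated question or named item.

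The withdrawal count of about 5 assumes that pilot rates carry over. It rests on two events, one in each arm, and is compatible with anything from about 1 to 18. The firmer conclusion is qualitative: non-gastrointestinal symptoms that do not lead to withdrawal would not be systematically elicited. The point should be fixed before enrolment, because unasked symptoms cannot be recovered later. It does not bear on sample size or power.

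**What to change.** 1. **Nutritional Supplement:** add one open question to each existing call, for example: Since the last call, have you had any new symptom or health problem, or any unplanned clinic or hospital visit? Log each answer with onset date and outcome.
2. **Infant outcomes:** name miscarriage, stillbirth and neonatal death among the items taken from the medical record.
3. **Hypotheses and Analyses:** add a table of side effects (including the gastrointestinal answers already collected), adverse events, pregnancy losses, and reasons for withdrawal or exclusion, by randomised arm, with all randomised women as the denominator.

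The cost is slightly longer calls, more minor events to log, three record items and one table. Visits, dose and sample size are unchanged. If a separate safety document already provides for collection, cross-reference it here and add only the table.

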There are two reasons for our focus on African American women. First, as described above, African American women are disproportionately represented among families living in inner-city poverty and have the highest rates of suboptimal birth outcomes in the U.S. (Giscombé & Lobel, 2005). Second, there are racial differences in cortisol reactivity to

stress and pregnancy (De Santis et al., 2007; Glynn et al., 2007; Wilcox et al., 2005) and in the genes regulating cortisol (Baerwald et al., 1999). Given the scope of the proposed study and the potential to generate data that can be translated into reductions in health disparities, we chose to study African Americans only, but acknowledge that it will be important to test racial and ethnic differences in maternal and infant response to DHA supplementation during pregnancy.

Women will be randomly assigned to receive the omega-3 nutritional supplement (n = 112) or a corn and soybean oil placebo (n = 56) beginning at enrollment and up through the end of pregnancy. In the proposed design we allocate the number of participants to groups to optimize power to test the hypotheses. We expect greater variability in the independent measure (i.e. DHA level) and dependent measures (e.g., stress reactivity) in participants in the experimental group than those in the control group given anticipated differences in uptake and metabolism. Thus, we plan to enroll a higher number of participants in the experimental group than in the control group to adequately capture that variability (Cox, 1958). Participants and investigators will be blinded to the group to which they have been assigned. Treating clinicians will identify demographically eligible participants who will be contacted by research staff for further screening. Participants who meet the inclusion and exclusion criteria will then be scheduled for the baseline visit.

Participants will be reimbursed on an accelerated schedule with \$100 for their first visit and an increase in payments by \$25 for each subsequent visit, ending with a \$250 payment for the last post-partum visit. Participants will receive incentives in between visits including water bottles, tote bags, newborn t-shirts, etc. They also will be reimbursed with \$10 to cover travel costs for each visit.

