Maternal Inflammatory Markers. Blood levels of TNF-α and IL-6 will be determined via enzyme-linked immunoassay (ELISA) from the blood draws at each of the four prenatal visits. The CoV for both cytokines is <5%. CRP will be determined turbidmetrically (CoV, 3.0%). All samples will be assayed in the Heinz Laboratory of the Graduate School of Public Health, which has CLIA certification and is enrolled in the proficiency-testing program organized by the College of American Pathologists.

Maternal Stress Response. Following published recommendations for assessing physiological stress reactivity during pregnancy (de Weerth & Buitelaar, 2005), the *Trier Social Stress Test* (TSST; Kirschbaum, 1993) will be used as stressful stimulus in the laboratory. The TSST consists of a three-minute preparation time, followed by a 3-minute speech (job interview), and then a 3-minute mental arithmetic task. The latter two tasks are performed in front of a video camera and an audience. The TSST reliably elicits a cortisol response, even in pregnant women (Nierop et al., 2006a; 2006b).

Saliva will be collected at five time points: 20 minutes and 5 minutes pre-TSST, and 20, 40, and 50 minutes post-TSST. To collect saliva samples, an absorbent, unflavored dental roll is applied to the tongue, cheek, and gums for several minutes. Flow rate will also be timed. The dental roll will then be returned to the plastic salivette and labeled. Samples will be immediately transferred to a freezer and stored at -80° C until assayed. On the day of testing, samples will be thawed, centrifuged at 3,000 rpm for 10 minutes and a clear sample will be pipetted into appropriate test wells. All samples from each subject will be assayed in the same batch to minimize variability, and will be assayed with reagents from the same lot. Samples with sufficient saliva will be assayed in duplicate for cortisol using the Salimetrics protocols. The cortisol assay has

an average between-assay variance of 3.9% and 7.1%, and the average within-assay variance is 6.7% and 6.9% for high and low concentrations, respectively.

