Measure	Variables		16-20 wks	24-30 wks	34-36 wks	1 month	4 months	9 months
Maternal Psychosocial Stress								
Perceived stress	Perceived stress Total score from PSS		1	>	>	>	>	1
Life events	Life events Total score from DLC		1	1	1	1	1	1
Depressed mood		1	1	1	1	1	1	1
Anxiety Total score from STAI		/	1	1	1	1	/	1
Maternal Stress Response								
Reactivity to TSST	Cortisol; HR, BP	>	1	>	>			
DHA Levels								
Blood draw	DHA levels in red blood cells	>	1	1	1			
Maternal Inflammatory Markers								
Blood draw	CRP; IL-6; TNF-α	>	1	>	>			
Infant Outcomes								
Birth	Birth weight, gestational age, Apgar, meconium					1		
Neurodevelopmental functioning	NBAS, BSID					1	1	1
Stress reactivity	Cortisol response to NBAS, FFSF					>	>	1
Temperament	IBQ; IBQ-R – short form						1	1

Table 1. Overview of main study variables

Hypotheses and Analyses

Hypothesis 1. DHA supplementation will improve maternal health during pregnancy among African American women living in urban poverty. Women who receive DHA supplementation will report lower levels of self-reported perceived stress over time, despite a lack of change in exposure to environmental stressors. Inflammatory markers including C-reactive protein (CRP), IL-6, TNF-α will be lower among women receiving DHA supplementation compared to placebo. To test for significant differences in perceived stress and inflammatory marker levels we will use repeated measures ANOVA (rmANOVA) with supplement group as the between-subjects factor and visit as a within-subjects factor. The interaction between group and time will be of particular interest. A Greenhouse-Geisser sphericity adjustment (Geisser & Greenhouse, 1958) will be employed. If any of the dependent measures exhibit a non-normal distribution (e.g. CRP), then a suitable data transformation will be used. Changes over time in prenatal levels of depression and anxiety will also be assessed using rmANOVA. Scatter plots and box plots of the data will be used to further explore these relationships. Plots of the data also will be examined to detect nonlinear time effects in addition to using orthogonal polynomial contrasts to formally test for quadratic and cubic effects. The association between change in DHA levels in the blood from baseline to the last prenatal visit and change in perceived stress will be examined using linear regression models.

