Response to a controlled stressor including cortisol, blood pressure, and heart rate will be better modulated among women receiving DHA supplementation than among women who do not, as demonstrated by a lower peak response and more rapid recovery to baseline. Differences in stress reactivity (i.e., cortisol levels, blood pressure, and heart rate) will be tested using two complementary approaches. First, we will use rmANOVA with supplement group as the between-subjects factor and timing of measurement (e.g. 20 minutes and 5 minutes pre-TSST, and 20, 40, and 50 minutes post-TSST for cortisol) as the within-subjects factor for each of the 4 prenatal visits separately. The interaction between group and time will be tested. For further interrogation of these changes, a random intercept, random slope mixed-effects model will be fit and results compared to the rmANOVA results. Second, the area under the curve (AUC) will be calculated for each participant at

each visit. Since primary interest is in assessment of changes over time, the AUC_I (area under the curve with respect to increase) will be used (Pruessner et al., 2003). Differences in these AUCs will be tested using rmANOVA with supplement group as the between-subjects factor and visit as the within-subjects factor. The interaction between group and visit will also be included to explore whether the magnitude of the difference between the groups is affected by the length of DHA supplementation. A Greenhouse-Geisser sphericity adjustment will be employed in both rmANOVA analyses. For further exploration of the patterns over time, a cluster analysis using the AUCs at each visit will be performed, and the association between the "change groups" formed from this cluster analysis and supplement group will be determined using a chi-square or Fisher's exact test. Log-transformed cortisol values will be used if appropriate. Also, time of collection and prenatal depression and anxiety will be controlled for in these analyses if needed.

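### The visit factor in the Hypothesis 1 repeated measures ANOVAs appears to include the pre-supplementation visit, with no baseline covariate; this dilutes the group main effect, chiefly for the cortisol AUC

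*Combined protocol and SAP*

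**What the plan says.** All references are to the combined protocol and SAP.

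- **Perceived stress, CRP, IL-6, TNF-α** (Hypotheses and Analyses, Hypothesis 1): repeated measures ANOVA with "supplement group as the between-subjects factor and visit as a within-subjects factor". The plan adds: "The interaction between group and time will be of particular interest".
- **Cortisol AUC** (same section, second approach to stress reactivity): "Differences in these AUCs will be tested using rmANOVA with supplement group as the between-subjects factor and visit as the within-subjects factor". Here the interaction has a lesser role: "The interaction between group and visit will also be included to explore whether the magnitude of the difference between the groups is affected" by how long supplementation has lasted.
- **Covariates for the stress-response analyses**: "time of collection and prenatal depression and anxiety will be controlled for in these analyses if needed". The baseline value of the outcome is not listed here or elsewhere in Hypothesis 1.
- **Visits**: inflammatory markers come "from the blood draws at each of the four prenatal visits" (Maternal Inflammatory Markers). On the first visit, the Participants section says: "Participants who meet the inclusion and exclusion criteria will then be scheduled for the baseline visit". Supplementation runs "beginning at enrollment and up through the end of pregnancy". Methods states that the prenatal visits share one protocol.

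The plan does not say which visits make up the visit factor.

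**The concern.** If the first visit is a level of the factor, the group main effect averages four between-group differences, one of which must be zero apart from chance because no supplement has yet been taken. The main effect then understates the effect of supplementation, and any chance imbalance at baseline stays in the estimate. The baseline value, which is already collected and could explain variation between women, is not used for that purpose.

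This matters most for the AUC. Its interaction is included only to explore, so the main effect is the comparison on which a conclusion would rest.

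**Working it through.** **Is baseline a level?** The plan does not say so, but three things point that way. The visit factor is unrestricted. Stress reactivity is analysed at four prenatal visits, the first being baseline. The pilot analysis of arrival cortisol at baseline, 24 and 30 weeks reports a Greenhouse-Geisser numerator df of 1.74. There is one value per visit, so a df above 1 needs at least three visits, which includes baseline.

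**Inputs from Power Calculations for Hypothesis 1.** 108 and 54 women; two-sided 0.05. Perceived stress 27.5 (SD 3.4) vs 29.3 (3.1), difference 1.8. AUC -4.5 (SD 3.9) vs -8.1 (6.1), difference 3.6.

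- Pooled variance, perceived stress: (107×11.56 + 53×9.61)/160 = 10.91, SD 3.30.
- Pooled variance, AUC: (107×15.21 + 53×37.21)/160 = 22.50, SD 4.74.
- h = 108×54/162 = 36.

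**Assumed, because the documents give no figure.** Between-visit correlation ρ = 0.3/0.5/0.7, compound symmetry, sphericity epsilon 1, complete data.

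**Step 1: the plan's own figures.** An unadjusted comparison at one visit gives 90.1% for perceived stress by noncentral t (90.5% by the normal approximation) and 97.7% to 99.5% for the AUC, depending on how the unequal SDs are handled. The stated >90% and >95% reproduce. They describe a single-visit comparison, not the rmANOVA.

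**Step 2: dilution.** For a difference δ at all three later visits, the main effect estimates (0 + δ + δ + δ)/4 = 0.75δ: 2.7 instead of 3.6 for the AUC, and 1.35 instead of 1.8 for perceived stress.

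**Step 3: power formulas.** Let d be the differences at the four visits and m their mean.

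- Main effect: λ = h·m² / [SD²(1+3ρ)/4], on 1 and 160 df.
- Group × visit: λ = h·Σ(d−m)² / [SD²(1−ρ)], on 3 and 480 df.
- Final visit adjusted for baseline: λ = h·d₄² / [SD²(1−ρ²)], on 1 and 159 df.
- Unadjusted mean of the three later visits (to isolate the role of baseline): λ = h·m₃² / [SD²(1+2ρ)/3], on 1 and 160 df, with m₃ the mean of the three later differences.

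Example, AUC, effect at the last two visits, ρ = 0.5. Main effect: m = 1.8, variance 22.50×2.5/4 = 14.06, λ = 36×3.24/14.06 = 8.30, power 82%. Adjusted final visit: λ = 36×12.96/(22.50×0.75) = 27.65, power above 99%.

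**AUC, power (%) at ρ = 0.3/0.5/0.7**

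| Visits with the 3.6 difference | Planned main effect | Unadjusted mean, three later visits | Baseline-adjusted final visit |
|---|---|---|---|
| All three later visits | 99.8/99.0/97.1 | all >99 | all >99 |
| Last two | 91/82/73 | 99/96/92 | all >99 |
| Last only | 38/30/25 | 54/46/39 | all >99 |

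The third column shows how the loss divides. With an effect at the last two visits, most of the shortfall disappears when baseline is dropped. With an effect at the last visit only, most of it comes from averaging in later visits that are themselves null.

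**Perceived stress, power (%) at ρ = 0.3/0.5/0.7**

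| Visits with the 1.8 difference | Planned group × visit | Baseline-adjusted final visit |
|---|---|---|
| Last only | 82/93/99.6 | 93/96/99.5 |
| Last two | 92/98/>99.9 | 93/96/99.5 |
| Linear build-up to 1.8 | 68/83/97 | 93/96/99.5 |

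For the last-visit-only pattern the gain is about 11, 3 and 0 points. For the last two visits the interaction does about as well at ρ = 0.3 and better above that. The gain is larger only if the effect builds linearly. A 5,000-run simulation for perceived stress at ρ = 0.5 agreed with the formulas within 1 point.

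**The case against.** A group-by-visit rmANOVA is a valid analysis of a randomised trial, so this is a matter of efficiency and of what is estimated, not of a biased test. For perceived stress and the inflammatory markers, the plan points to the interaction, which is not diluted and takes each woman's baseline as her own reference. For the AUC, the interaction is in the model too, and would have 98.5% power or more for a last-visit-only effect. The separate-visit rmANOVAs of cortisol are not diluted either. All of this stands, and it confines the clear loss to the main-effect test. It does not rescue the AUC comparison as written, because the plan gives that interaction only an exploratory role.

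The correlations are assumed, and those for the AUC may be low: the plan itself cites habituation between the first and second stress tests. A low correlation shrinks the gain from adjustment but leaves the dilution in place. At ρ = 0.1 the AUC main effect has 51% power for a last-visit-only difference, against 99.5% for the adjusted final visit.

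A reader might infer three stronger things that the documents do not support.

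- *That baseline is ignored altogether.* The interaction uses it, and a planned regression relates change in perceived stress to change in DHA from baseline. Only the covariate is absent.
- *That the first visit precedes randomisation.* The documents show only that it precedes supplementation; they do not place assignment before or after the baseline measurements.
- *That adjustment lifts perceived-stress power from the stated >90% to 93/96/99.5%.* That benchmark is an unadjusted single-visit comparison, not the planned analysis. Against the planned interaction, the last-visit-only gain falls as ρ rises and vanishes at 0.7.

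**Conclusion.** The point holds, with moderate confidence, and should be addressed. It is strongest for the AUC main effect, which recovers exactly three quarters of a constant effect and retains chance baseline imbalance. Power remains high if the effect is constant. It falls materially for the late pattern seen in the pilot, where neither perceived stress nor the cortisol response differed at 24 weeks and both did at 30. For perceived stress and the markers, adjustment brings a modest gain for late effects and sometimes none; the marker outcomes were not computed separately.

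The conclusion rests on an inferred reading of the visit factor and on the assumptions listed in the working. The pooled SD is somewhat favourable for the AUC, because the larger SD (6.1) belongs to the smaller arm. Last observation carried forward could also place baseline values in later visits and add dilution; that was not quantified.

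**What to change.** - State which visits form the visit factor in each Hypothesis 1 rmANOVA.
- For each maternal outcome with a baseline value, replace the group main-effect test with a longitudinal model of the post-baseline visits containing the baseline value, group, visit and group × visit. A constrained longitudinal model is an alternative.
- Pre-specify the baseline-adjusted group difference at 34-36 weeks as the reported contrast. An average over all later visits is not a substitute: for a last-visit-only perceived-stress effect, its baseline-adjusted power is only 37/39/49% at ρ = 0.3/0.5/0.7.
- Keep the group × visit test.

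The cost is plan wording; no new data are needed. The one drawback is that a single-visit contrast can be slightly less powerful than the omnibus interaction for some patterns, for example 96% against 98% for a perceived-stress effect at the last two visits with ρ = 0.5.
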